 or possibly linked to exposure to the study medication.

Additional information on the exposure during pregnancy may be requested. Monitoring of cases in which the outcome is birth will be treated on a case by case basis (for example, monitoring of infants born pre-term in order to identify any developmental delays).

In cases of paternal exposure, an information form for pregnant partners will be given to the patient participating in the study for his partner. It must be documented that this form has been given to the patient participating in the study to be passed on to his partner.

Exposure during breastfeeding

Cases of exposure during breastfeeding must be reported, regardless of whether there is an associated AE.

A notification of exposure during breastfeeding must not be submitted when a Pfizer/Novartis product is specifically indicated for use in breastfeeding women (e.g. vitamins) and it has been administered in line with the MA.

[figure not shown]
However, if the baby presents with an associated AE on administration of such a product, the AE must be declared as exposure during breastfeeding.

Medication error

A medication error is understood to be any unintended error in prescription, dispensing or administration of a medication that may lead to inappropriate medication use or patient harm while the medication is in the control of a healthcare professional, patient or consumer. Such events may be related to professional practice, healthcare products, or procedures and systems, including: prescribing, order communication, product labelling, packaging and nomenclature, compounding, dispensing, distribution, administration, education, monitoring and use.

Medication errors include:

- Near-misses, whether or not these involve a patient directly (for example, inadvertent or mistaken administration, which is the accidental use of the product outside of its indication or prescription by a healthcare professional or a patient/consumer)
- Confusion concerning the name of a product (for example, trade name, brand name).

The investigator must declare the following medication errors to the Pfizer/Novartis Pharmacovigilance Departments, regardless of whether there is an associated AE/SAE:

- Medication errors involving patient exposure to the product, regardless of whether the medication error is accompanied by an adverse event or not.
- Medication errors that do not directly involve a patient (for example, potential medication errors or near-misses). When a medication error does not involve patient exposure to the product, the following are the minimum criteria for a case of medication error:
 - Identifiable notifier
 - Suspected product
 - Medication error

Overdose, Misuse, Extravasation

Cases of overdose, misuse and extravasation associated with the use of a Pfizer/Novartis product must be declared to the Pfizer/Novartis Pharmacovigilance Departments by the investigator, regardless of whether there is an associated AE/SAE or not.

Lack of efficacy

Cases of lack of efficacy of a Pfizer/Novartis product must be declared to the Pfizer/Novartis Pharmacovigilance Departments by the investigator, regardless of whether there is an associated AE/SAE or not; or indication for a Pfizer/Novartis product.

Occupational exposure

Cases of occupational exposure to a Pfizer/Novartis product must be declared to the Pfizer/Novartis Pharmacovigilance departments by the investigator, regardless of whether there is an associated AE/SAE or not.

The serious or non-serious adverse event monitoring form must be sent by fax within 24 hours to the Novartis Pharmacovigilance Department on the following number: [name] or to the Pfizer Pharmacovigilance Department on the following number: [name].

As part of the enhanced monitoring of specific risks as defined in the Risk Management Plans for AFINITOR (Afinitor RMP, V 9/8) and for SUTENT (SUTENT RMP V14.0) respectively, the Novartis/Pfizer Pharmacovigilance Departments may need to send to the doctor or to any other involved healthcare professional a targeted questionnaire about these events and this will need to be returned to the Novartis/Pfizer Pharmacovigilance Department once it has been completed.

Collection and declaration of adverse events to Pharmacovigilance departments – Retrospective data

This protocol also requires the investigator (or an individual under the investigator's responsibility) to carry out a review of so-called "unstructured" patient data: unstructured data is medical data, including written or visual descriptions of medical information such as medical files, doctors' notes, neurological tests, radiography, or "comments" fields in a database.

the protocol, i.e.:

The person in charge of this review must enter on the electronic CRF all serious and non-serious adverse events (AE) that are clearly related to a Pfizer medication or to Everolimus that may appear in the data that are reviewed (defined by patient population and by the specific study phase of the protocol), if they meet the conditions for retrospective declaration of (S)AE as defined in § 5.2.2 of

[figure not shown]
- If the treatment ongoing at enrolment is Everolimus, enter the following in the electronic CRF so that the CRO in charge of the study can submit a declaration to the Pharmacovigilance departments:
 - (S)AE(s) clearly related to Everolimus that occurred between starting Everolimus and enrolment.
 - (S)AE(s) clearly related to a Pfizer product that occurred between starting the first line treatment for the illness and enrolment
- For all other treatments ongoing at enrolment (Sunitinib, chemotherapy, somatostatin analogues, radionuclide therapy or interferon alpha), retrospective declaration in the electronic CRF is required, so that the CRO in charge of the study can submit a declaration to the Pfizer Pharmacovigilance Department, in the following cases:
 - (S)AE(s) clearly related to a Pfizer product that occurred between starting the first treatment line for the illness and enrolment.

The temporal relationship between administration of the medication and the adverse event cannot be used as the basis for a judgement of whether the event can be attributed to the medication, and instead this must be founded on a health professional making an unquestionable determination of causality that will establish a link between the medication and the AE.

All serious and non-serious adverse events as well as specific situations that need to be declared to the pharmacovigilance departments that are identified based on the data examined must, if they meet the conditions for retrospective declaration of (S)AE, be recorded in the electronic CRF.

These events will be declared to the Pharmacovigilance Departments of Pfizer and Novartis directly via the eCRF (there is no need for any additional submission) using the NIS AEM Report Form and following the requirements applicable to the reporting of adverse events to the pharmacovigilance departments concerned:

- All serious and non-serious adverse events must be declared to the Pharmacovigilance Departments concerned as follows:
 - Serious and non-serious adverse events clearly related to a Pfizer medication will be reported to the Pfizer Pharmacovigilance Department by the CRO within 24 hours of the event coming to light (entered on the electronic CRF by the investigating site)
 - Serious and non-serious adverse events clearly related to everolimus will be reported to the Novartis Pharmacovigilance Department by the CRO within 24 hours of the event coming to light (entered on the electronic CRF by the investigating site)
- Situations involving exposure during pregnancy via the mother or father in which the outcome is unknown must be declared to the Pharmacovigilance Departments within 24 hours of the event coming to light:

- For exposure to a Pfizer product: report to Pfizer Pharmacovigilance Department
- For exposure to everolimus: report to Novartis Pharmacovigilance Department
- Situations concerning exposure during breastfeeding, medication errors, dispensing errors, medication administration errors or accidental exposure to a medication, overdose, misuse, abuse, interaction with another medication or food, lack of efficacy, off-label use, withdrawal or rebound symptoms, extravasation or occupational exposure associated with the use of a Pfizer product or everolimus must be declared to the Pharmacovigilance Departments concerned as follows:
 - All situations associated with use of a Pfizer medication will be reported to the Pfizer Pharmacovigilance Department within 24 hours of the situation coming to light
 - All situations associated with use of everolimus will be reported to the Novartis Pharmacovigilance Department within 24 hours of the situation coming to light

For adverse events clearly related to or associated with the use of a Pfizer product/everolimus, the data entered in the medical file will constitute all of the known clinical information concerning these adverse events. There will be no follow-up concerning these adverse events.

All members of staff at the CRO in charge of monitoring the study must meet the requirements of Pfizer and Novartis in terms of training in: "Your Reporting Responsibilities: Monitoring the Safety, Performance and Quality of Pfizer Products (Multiple Languages)" (Pfizer) and 5 P training, which is validated through a specific test in "Management of local interventional studies - DVL.OC.P.0002 (Novartis)" as well as any other additional training deemed to be useful. This training will be provided to all CRO staff before the study begins. All training will include a "certificate of training" (signed by the person trained) as confirmation, and this must be kept in an accessible format. Copies of all signed training certificates must be provided to Pfizer and to Novartis.

8. **Data Processing**

8.1. **Determining the sample size**

Calculating how many patients to include

The calculation of the number of patients needed is based on the primary objective of describing morbidity and mortality evaluated specifically in terms of progression-free survival and overall survival.

The calculation is based on the expected precision of the estimate of median survival (confidence interval).

An estimate of the variance of S(t) (Kaplan Meier estimator) is given using Greenwood's formula:

$$\hat{Var}[\hat{S}(t)] = [\hat{S}(t)]^2 \sum_{j:t_j \leq t} \frac{d_j}{n_j(n_j - d_j)}$$

Where t_j is the event time, d_j is the number of events in this time and n_j is the population at risk

With the hypothesis that there is no right-censoring before the median and only a single event by the event time, it is possible to simplify Greenwood's formula for median survival as follows:

$$\hat{Var}[\hat{S}(t)] = \frac{0.5^2}{n}.$$

We may then calculate different variances and CI of S(t) depending on n and also the precision.

s(t) ²	n	variance (s(t)²/n)	Lowest CI	Highest CI	precision
	75	0.0033	0.38	0.61	0.113
	100	0.0025	0.40	0.59	0.098
	125	0.0020	0.41	0.58	0.088
0.25	150	0.0016	0.42	0.58	0.080
0.25	200	0.0012	0.43	0.56	0.069
	225	0.0011	0.43	0.56	0.065
	250	0.0010	0.43	0.56	0.062
	360	0.0010	0.44	0.55	0.052

[figure not shown]
For precision of 5%, 360 patients must be included.

Furthermore, in view of:

- The target population, estimated at 150 170 cases per year,
- The prevalence of the treatment groups of interest and the need to stratify enrolments across the treatment sub-groups,
- The inclusion criteria,

The calculation of how many patients to include in the study must find a balance between the statistical calculations and the feasibility of the study. Therefore, according to the data available, a total of 150 patients enrolled over a period of around 2 years seems to be a realistic target. The inclusion of 150 patients in total would allow the median survival (progression-free or overall) to be estimated with a precision of around 8%.

It should be noted that in the analyses of the sub-groups (targeted therapy, other treatments) the median will be estimated with less precision since the totals in each stratum will be lower. For example, if we assume a balanced distribution of patients between the targeted therapies and other treatments groups, or 75 patients per group, precision will be 11%.

Where the other descriptive objectives of the study are concerned, the estimated number of patients rests on the precision of the relative frequency based on the following formula:

$$n = \frac{\varepsilon^2}{i^2} p(1-p)$$

In the absence of a hypothetical value of expected relative frequencies, with the hypothetical maximum value of a relative frequency of 50%, an α risk = 5% and a power (1- β) = 80%, 384 patients will need to be included.

According to the relative frequencies observed and the patient numbers (overall or by treatment stratum) the following precision can be expected:

Relative	Expected pr	ecision			
frequencies observed	n=75	n=150	n=200		
10 – 90	6.8	5.3	4.2		
20 - 80	9.1	7.0	5.5		
30 – 70	10.4	8.0	6.4		
40 - 60	11.1	8.6	6.8		
50	11.3	8.8	6.9		

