4.2. Calculation of the number of subjects

The number of subjects required is calculated based on the primary descriptive objective of morbidity and mortality assessed in particular by progression-free survival and overall survival.

The calculation is based on the expected precision of the estimate of median survival (confidence interval).

An estimation of S(t) variance (Kaplan Meier estimate) is given by the Greenwood equation:

$$\hat{Var}[\hat{S}(t)] = [\hat{S}(t)]^2 \sum_{j:t_j \le t} \frac{d_j}{n_j(n_j - d_j)}$$

Where tj is the events time, dj is the number of events at these times and nj is the number of patients at risk.

Assuming no right censoring before the median and the occurrence of a single event by event time, the Greenwood equation can be simplified for median survival:

$$\hat{Var}[\hat{S}(t)] = \frac{0.5^2}{n}.$$

Different variances and the CI of S(t) can therefore be calculated depending on n and therefore on precision.

s(t) ²	n	Variance (s(t)²/n)	Lower CI	Upper CI	Precision
0.25	75	0.0033	0.38	0.61	0.113
	100	0.0025	0.40	0.59	0.098
	125	0.0020	0.41	0.58	0.088
	150	0.0016	0.42	0.58	0.080
	200	0.0012	0.43	0.56	0.069
	225	0.0011	0.43	0.56	0.065
	250	0.0010	0.43	0.56	0.062
	360	0.0010	0.44	0.55	0.052

A total of 360 patients will need to be included to achieve a precision of 5%.

Given:

- The estimated target population of 150 to 170 cases per year,
- The prevalence of the treatment groups of interest and need to stratify the inclusions on treatment subgroups,
- The study inclusion criteria.

The number of patients to be included in the study must be calculated balancing the statistical calculations against the feasibility of the study. According to the data which are available, a number of 150 patients included over a period of 2 years would appear to be a feasible objective. Inclusion of a total of 150 patients would allow an estimate of median survival (progression-free survival, or overall survival) with a precision in the region of 8%.

It should be noted that analyses in the subgroups (targeted therapy, other treatments) enable the median value to be estimated with greater inaccuracy as the numbers in the stratification groups are smaller. Considering for example a balanced distribution of patients between the targeted therapy and other treatments groups ie, 75 patients per group, precision will be 11%.

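### The 8% and 11% precision claimed for median survival are percentage-point half-widths of a survival probability at S = 0.5, and two sample-size table entries are misprinted

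*Protocol*

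**What the plan says.** Protocol 8.1 opens by declaring its target: "The calculation is based on the expected precision of the estimate of median survival (confidence interval"). It then simplifies Greenwood's variance to 0.5²/n, relying on an assumption: "With the hypothesis that there is no right-censoring before the median", plus one event per event time. The table is introduced by "We may then calculate different variances and CI of S(t) depending on n and also the precision". Its n = 150 row gives a variance of 0.0016, limits of 0.42 and 0.58, and a precision of 0.080. Its n = 75 row gives a precision of 0.113.

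The conclusion drawn is that 150 patients "would allow the median survival (progression-free or overall) to be estimated with a precision of around 8"%, and for the two treatment groups "75 patients per group, precision will be 11"%. The protocol summary repeats both figures, and Protocol 9.5 repeats the 8%. SAP 4.2 has the same derivation and table ("Different variances and the CI of S(t) can therefore be calculated depending on n and therefore on precision") and concludes that 150 patients allow "an estimate of median survival (progression-free survival, or overall survival) with a precision in the region of 8"%, with 11% per group. SAP 6.5 repeats the 8%.

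For the other descriptive objectives, Protocol 8.1 adds a table of proportions ("the following precision can be expected") whose n = 150 column reads 5.3, 7.0, 8.0, 8.6, 8.8. The same column in SAP 4.2 reads 4.8, 6.4, 7.3, 7.8, 8.0.

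**The concern.** The derivation concerns the height of the survival curve where it crosses 0.5. The conclusion concerns the time at which it crosses. These are different quantities on different scales, and converting one to the other needs the slope of the curve. SAP 5.5.1 reports the median in months, so a reader will naturally take 8% to mean a margin of about 8% on that time. No such margin has been calculated.

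Together with feasibility, this figure is the stated basis for 150 patients, and it appears in five places. The protocol summary, Protocol 9.5 and SAP 6.5 carry no table that would show the true scale.

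The two table faults are separate and simpler. The two documents disagree on the n = 150 proportions column, and the n = 360 variance does not agree with the precision in its own row.

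**Working it through.** **Inputs.** 95% intervals, so z = 1.96. S = 0.5 and Var = 0.25/n, from Protocol 8.1 and SAP 4.2.

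**Step 1: reproduce the stated precision.** Half-width = 1.96 × √(0.25/n).

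| n | 0.25/n | variance printed | half-width | precision printed |
|---|---|---|---|---|
| 75 | 0.00333 | 0.0033 | 0.113 | 0.113 |
| 125 | 0.00200 | 0.0020 | 0.088 | 0.088 |
| 150 | 0.00167 | 0.0016 | 0.080 | 0.080 |
| 250 | 0.00100 | 0.0010 | 0.062 | 0.062 |
| 360 | 0.00069 | 0.0010 | 0.052 | 0.052 |

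The precision column reproduces throughout. At n = 150 the interval is 0.5 ± 0.080, that is 0.42 to 0.58, as printed. The 8% and 11% are therefore percentage points of S(t). SAP 4.2 confirms the scale: its table for ordinary proportions gives the same 8.0 (n = 150) and 11.3 (n = 75) in the 50% row.

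**Step 2: what this means for the median as a time.** The documents assume no survival curve, so this step is an illustration. Take exponential survival with no censoring and invert the limits of S:

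- n = 150: −ln(0.58)/ln 2 = 0.79 and −ln(0.42)/ln 2 = 1.25, so the interval is about 0.79 to 1.25 times the median.
- n = 75: limits 0.613 and 0.387 give about 0.71 to 1.37 times the median.

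Raising these multiples to the power 1/k gives the Weibull case with shape k. For k from 0.8 to 1.3, the n = 150 interval runs from 0.74–1.32 to 0.83–1.19, and the n = 75 interval from 0.65–1.48 to 0.77–1.27. None of these is close to ±8% or ±11% of the median.

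**Step 3: proportions table.** Half-width in points = 196 × √(p(1−p)/n).

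| p | protocol, n = 150 | SAP, n = 150 | formula, n = 150 | formula, n = 125 |
|---|---|---|---|---|
| 10% | 5.3 | 4.8 | 4.80 | 5.26 |
| 20% | 7.0 | 6.4 | 6.40 | 7.01 |
| 30% | 8.0 | 7.3 | 7.33 | 8.03 |
| 40% | 8.6 | 7.8 | 7.84 | 8.59 |
| 50% | 8.8 | 8.0 | 8.00 | 8.77 |

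The protocol's column is the n = 125 result. Solving each printed entry for n gives about 123, 125, 126, 125 and 124. The protocol also contradicts itself: its survival table prints 0.080 for n = 150 and 0.088 for n = 125 by the same arithmetic. The entries are 0.5 to 0.8 points too wide, about 9–10% in relative terms (√(150/125) = 1.095). The n = 75 and n = 200 columns agree with the formula within rounding in both documents.

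**Step 4: n = 360 variance.** 0.25/360 = 0.00069, against 0.0010 printed, which is 44% too high (0.0010/0.000694 = 1.44). A variance of 0.0010 would give 1.96 × √0.0010 = 0.062, but the row prints 0.052. Working back, (0.052/1.96)² = 0.0007. The printed variance is the n = 250 value. Truncation does not explain it, because 0.00069 truncates to 0.0006.

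**The case against.** The numbers 8 and 11 are correct, and the table beside them shows their scale. The text could be using median survival as shorthand for the curve at S = 0.5, and an interval for the median is normally obtained by inverting the interval for S(t) there. On that view the fault is a missing label. Feasibility set the size in any case, recruitment is closed, and no reported estimate depends on these figures. The proportions error exists only in the protocol and overstates imprecision. The n = 360 row has the right interval and precision, and 360 was not adopted.

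Most of this is true, and it limits the consequence. It does not rescue the sentences. Inverting the interval for S(t) gives a margin in time that depends on the curve, and that step was never taken. SAP 6.5 concedes only that left truncation is ignored; it does not correct the scale.

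One further objection concerns the remedy. Moving the claim to 24-month rates needs no censoring before 24 months, which is more than the documents assume. SAP 6.1.3 also says that patients who started treatment two years before the study do not contribute to the two-year rate. This stands as a reason for an explicit caveat: ±8 and ±11 points assume the full 150 or 75 patients contribute, with no censoring or late entry.

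**Conclusion.** The concern holds as a misstatement that should be corrected. The figures are right as ±8.0 (n = 150) and ±11.3 (n = 75) percentage points of S(t) at S = 0.5, with no censoring or late entry. They are wrong as the precision of median survival, which the documents do not derive. The time-scale multiples in the working rest on assumed exponential or Weibull curves and show only that the two scales differ materially. The two table errors follow directly from the documents' own formulas and need no assumption. Only the description of precision in the plan and the report is affected.

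**What to change.** 1. In the protocol summary, Protocol 8.1 and 9.5, and SAP 4.2 and 6.5, replace the concluding sentence with wording such as: *survival rates such as the 2-year PFS and OS rates will be estimated to within about ±8 percentage points (n = 150) or ±11 percentage points (n = 75) at S = 0.5, the least favourable value, before allowing for censoring and late entry, which widen these figures; no precision is claimed for the median survival time.* This suits SAP 5.5.1, which names the 24-month OS and PFS rates as the primary endpoint.
2. In the protocol summary, Protocol 8.1 and SAP 4.2, change the opening sentence so that the calculation is based on the expected precision of the Kaplan-Meier survival probability at S(t) = 0.5. In the sub-group sentences, refer to these rates instead of the median. Bring the closing sentence of SAP 6.5 into line.
3. In Protocol 8.1, replace the n = 150 proportions column with 4.8, 6.4, 7.3, 7.8, 8.0, as in SAP 4.2.
4. In both documents, correct the n = 360 variance to 0.0007. The variance column is otherwise truncated. If it is rounded throughout, the n = 150 entry becomes 0.0017; the n = 200 value is an exact tie (0.00125), so its entry depends on the rounding rule.

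The cost is wording and table entries only.

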8.2. Data management

A study-specific database will be created, tested and validated before data entry begins. A data validation plan will be set out and it will describe in detail the checks that will need to be performed for each variable as well as the list of authorised self-evident corrections.

A data processing manual will describe the procedures for data management (coding, entry, verification) as well as the questionnaires for the doctor and patient components.

Data will be entered by the participating doctors directly on the secure website. This will feed automatically into the study database. The database will be backed up on a daily basis. The key data will be set as compulsory fields in the electronic CRF in order to manage the proportion of missing data concerning the key parameters of the study.

The consistency of data will be checked exhaustively for all questionnaires in line with the rules that will be defined in the data validation plan. A significant part of the consistency checks will be carried out as the data is entered on the eCRF. The consistency checks set out by the data validation plan will separate out in particular cases concerning a request for clarification of data sent to a participating doctor; self-evident corrections and/or other cases of inconsistency or missing data will be handled in line with the decision-making rules agreed on with the scientific committee, which will be described in the data validation plan.

The database will be locked after a final quality assurance check.

Observational study protocol final version of 17/07/2018

While the study is ongoing, the original documents will be stored at the premises of the specialised service provider under contract to Novartis Pharma and Pfizer, and will only be accessible to authorised persons. They will then be sorted into archiving boxes and sent directly to the company in charge of archiving for Novartis Pharma and Pfizer.

